9. PHARMACOKINETIC ANALYSES

9.1. Endpoint / Variables

9.1.1. Drug Concentration Measures

Available concentration-time data for CAB and RPV will be presented in listings as specified in [Appendix 12](#): List of Data Displays and will be based on GSK Data Standards and statistical principles

10. VIROLOGY

10.1. Genotypic and Phenotypic Data

Available genotypic and phenotypic data at all collection timepoints will be presented by subject (separately for CVF and Non-CVF subjects), as specified in [Appendix 12: List of Data Displays](#).

11. OTHER ANALYSES

11.1. Endpoint / Variables

11.1.1. Study Visit length

Study Visit Length will be reported for all analyses including interim analyses, Month 12, and EOS. Details of the planned displays for study visit length data are provided in [Appendix 12](#) List of Data Displays and will be based on GSK Data Standard and statistical principle.

11.1.2. Pregnancy

Protocol amendment 02 allows for pregnant participants to remain on study and continue the use of study drug. Should any participants become pregnant while on study drug, pregnancy specific listings will be produced. Listings will include any adverse events, clinical lab results including HIV-1 RNA and plasma CAB & RPV concentrations, exposure to study drug during pregnancy, and pregnancy details including duration and outcomes reported by the participants including birth outcomes. Details of the planned displays are provided in [Appendix 12](#)

13. APPENDICES

13.1. Appendix 1: Schedule of Activities

The protocol also lists a schedule of activities for staff study participants (not listed here)

13.1.1. Protocol Defined Schedule of Events: Schedule of Activities for Patient Study Participants

Procedure	Screening ^a up to 35d	Intervention Period (Month)								Withdrawal ^m	Long Term Follow-up ⁿ
		Day 1	Month 1	Month 2	Month 4	Month 6	Month 8	Month 10 ^b	Month 12 ^b		
		Oral Lead-in	Dose 1 (D1)	Dose 2 (D2)	Dose 3 (D3)	Dose 4 (D4)	Dose 5 (D5)	Dose 6 (D6)	Dose 7 (D7)		
Written Informed consent	X										
Eligibility Verification	X										
Demography	X										
Physical Exam	X										
Medical history	X										
Current medical conditions	X										
Center for Disease Control and Prevention (CDC) HIV-1 Classification	X										

Procedure	Screening ^a up to 35d	Intervention Period (Month)								Withdrawal ^m	Long Term Follow-up ^a
		Day 1	Month 1	Month 2	Month 4	Month 6	Month 8	Month 10 ^b	Month 12 ^b		
		Oral Lead-in	Dose 1 (D1)	Dose 2 (D2)	Dose 3 (D3)	Dose 4 (D4)	Dose 5 (D5)	Dose 6 (D6)	Dose 7 (D7)		
Syphilis serology + reflex Rapid Plasma Reagin (RPR)	X										
CCI											
Symptom Directed Physical Exam and Medical Assessment ^c		X	X		X		X		X	X	X
HIV-associated Conditions, AE and serious adverse event (SAE) Assessments ^d , Con Meds	X	X	X		X		X		X	X	X
Vital Signs (blood pressure [BP], heart rate [HR]) ^e	X	X	X		X		X		X	X	
Weight, Height & body mass index (BMI) ^f	X	X	X		X		X		X	X	
Clinical Chemistry, Hematology and other Tests ^g	X	X	X	X	X		X		X	X	X

Procedure	Screening ^a up to 35d	Intervention Period (Month)								Withdrawal ^m	Long Term Follow-up ⁿ
		Day 1	Month 1	Month 2	Month 4	Month 6	Month 8	Month 10 ^b	Month 12 ^b		
		Oral Lead-in	Dose 1 (D1)	Dose 2 (D2)	Dose 3 (D3)	Dose 4 (D4)	Dose 5 (D5)	Dose 6 (D6)	Dose 7 (D7)		
HIV-1 RNA and plasma sample for storage ^h	X	X	X	X	X		X		X	X	X
CD4+ count	X	X	X	X	X		X		X	X	X
CD8+ cell count (will be reported at Baseline and Month 12)		X							X		
Urinalysis	X									X	X
Hepatitis Serology ^q	X										
Whole Blood PBMC ^p		X								X	
Prothrombin time (PT)/partial thromboplastin time (PTT)/international normalized ratio (INR)	X									X	X
Pregnancy Testing Urine (U) or Serum ^g	U	U	U	U	U	U	U	U	U	U	U
Notification of Interview ^t		X									

Procedure	Screening ^a up to 35d	Intervention Period (Month)								Withdrawal ^m	Long Term Follow-up ⁿ
		Day 1	Month 1	Month 2	Month 4	Month 6	Month 8	Month 10 ^b	Month 12 ^b		
		Oral Lead-in	Dose 1 (D1)	Dose 2 (D2)	Dose 3 (D3)	Dose 4 (D4)	Dose 5 (D5)	Dose 6 (D6)	Dose 7 (D7)		
Oral CAB + RPV Medication Dispensation		X									
CAB LA + RPV LA IM Treatment Administration ⁱ			X	X	X	X	X	X	X		
Participant Visit Reminder Contact	X	X	X	X	X	X	X	X			
Participant Contact Detail Confirmation	X	X	X	X	X	X	X	X			
Patient Toolkit ^s		X	X	X	X	X					
Record Visit Length ^j			X	X		X	X				
Contraception Counseling ^u										X	X
HAART dispensation ^v										X	X
Patient Questionnaires ^k			X		X				X		
Selected Patient Interviews ^l		X							X		

Procedure	Screening ^a up to 35d	Intervention Period (Month)							Withdrawal ^m	Long Term Follow-up ⁿ	
		Day 1	Month 1	Month 2	Month 4	Month 6	Month 8	Month 10 ^b			Month 12 ^b
		Oral Lead-in	Dose 1 (D1)	Dose 2 (D2)	Dose 3 (D3)	Dose 4 (D4)	Dose 5 (D5)	Dose 6 (D6)			Dose 7 (D7)
HIV and patient satisfaction (HIVTSQs)		X	X		X				X		
HIVTSQc									X		
Preference Question									X		

- a) A screening visit will be conducted within 35 days of Day 1. However, it is preferred for Day 1 to be conducted as soon as practical after all screening results are available.
- b) Continue this pattern for visits for the remainder of the study if needed, until CAB LA + RPV LA is locally approved and available. For example, Dose 8 will be conducted as per Dose 6, Dose 9 will be conducted as per Dose 7, Dose 10 will be conducted as per Dose 6 and so on. The exception to this pattern is that no questionnaires, study visit length collection, or patient interviews will be conducted after Dose 7 visit. See protocol Section 6.8.
- c) Physical exams should be conducted as part of normal routine clinical care but data will not be collected in the electronic case report form (eCRF) unless abnormalities are observed. Medical assessments include any decisions the study staff must make for participant management.
- d) AE and SAEs will not be proactively assessed at M 2, M 6 and M 10. However, all AEs and SAEs reported by study participants **must** be recorded in eCRF at all visits and reported within required timelines as per protocol Section 8.5.1 .
- e) Measure vital signs after about 5 minutes of rest in a semi-supine position.
- f) Height is collected at screening only.
- g) A (-) urine pregnancy test is required prior to oral lead-in at day 1 and prior to any injection and as required by Medical Monitor after a treatment interruption. A (+) urine test should be confirmed with a stat serum test. If (+), participant will need to be withdrawn. A Serum pregnancy test should be performed at any time pregnancy is suspected by the Investigator. Pregnant participants who remain in the study do not need pregnancy testing for the duration of the pregnancy See Protocol Appendix 15: Information and Guidance for Managing Pregnant Participants.
- h) Plasma for storage samples are collected for possible future analyses. Can be used for back-up in cases of loss/damage in transit, geno/pheno analyses for virologic failures. Only for women becoming pregnant and continuing on CAB LA+RPV LA as if pregnant a plasma HIV-1 RNA test and plasma for storage samples at Month 6 and Month 10 visits are required.
- i) All injections are 1 x CAB LA 600 mg IM + 1 x RPV LA 900 mg IM. Doses 1 and 2 are one month apart. Subsequent injections beginning at Dose 3 are every two months. The injections should be spaced approximately 2 cm from one another and from the site of any previous injection and/or any injection site

reaction. Bring RPV LA to approximately room temperature prior to injecting. Time and location of injection (right or left) as well as needle length used will be collected in the eCRF. **IM dosing is expected to occur on the same date of the month as determined by IM Dose 1 visit date, this is the Target Date; where possible, this first injection should be performed within 2 hours of taking the last oral regimen dose. For Dose 2, a dosing window of +0 / -7 days from the target visit date is stipulated. A (+ or -) 7-day window from the target date visit is stipulated for IM dosing beginning at Dose 3. All decisions regarding dose interruption/ resumption must be discussed with the Medical Monitor in advance.**

- j) Length of study visit from arrival until departure from clinic will be evaluated. Participant's time of arrival, actual start time of the appointment, and actual end time of the appointment will be collected in the eCRF.
- k) Questionnaires should be completed before receiving the injections.
- l) Interviews should be conducted before the PSP receives Dose 1 and within 4 weeks of receiving Dose 7. Interviews may be done in person, virtually, or by phone. A minimum of 6 patients per site will be selected for interviews.
- m) Withdrawal Visit - Conduct ~4 weeks after the last dose of investigational product (IP) if not entering Long-Term Follow Up and only if the participant has ongoing AEs or lab abnormalities at the last on-study visit. May be conducted by telephone.
- n) Participants receiving one or more injections with CAB LA and/or RPV LA will be assessed with clinic visits at months 3, 6, 9 and 12 during the Long-Term Follow-Up phase. The start of the 52-week follow-up period begins the day of the last CAB LA and/or RPV LA dose.
- o) See protocol Section 8.4.4 for list of tests
- p) Whole blood/PBMC collection samples may be used for virologic analyses. PBMCs will be collected at baseline Day1 and at Withdrawal.
- q) Hepatitis B (HBsAg), Anti-HBc, Anti-HBsAg, Hepatitis C (anti-HCVAb). A (+) anti-HCVAb will be followed by a confirmatory nucleic acid test for HCV RNA. HBV DNA will only be performed for participants with a (+) anti-HBc and (-) HBsAg and (-) anti-HBs (past and/or current evidence).
- r) Administer HIVTSQs in Day 1 before OLI initiation.
- s) At a minimum the study toolkit will be offered at the time pointed noted in the protocol Table 6. However, the toolkit items are intended to be used throughout the study.
- t) Notification of interviews may occur between Day 1 or during the 7 days after Day 1.
- u) Women of childbearing potential should continue to receive counselling on the need to use adequate contraception for the entirety of the Long-Term Follow-Up period.
- v) Investigators must discuss choice of HAART regimen and timing of initiation with the Medical Monitor before initiating.

13.2. Appendix 2: Assessment Windows

13.2.1. Definitions of Assessment Windows for Analyses

Laboratory data, vital signs, adverse events, and genotypic/phenotypic data will be assigned to assessment windows according to actual dates rather than the nominal visit labels as recorded on the eCRF or in the laboratory database.

Prior to visit slotting, assessments are first assigned to a study phase (Screening, Intervention Phase, Extension, or Long Term Follow Up) as defined in [Appendix 3](#).

According to the protocol, the nominal target study visit date will be based on the first injection, the Month 1 date. For instance, if Month 1 occurred on July 7th, all subsequent visits are expected to occur on the 7th of each month such that subsequent visits will be August 7th, September 7th, October 7th, etc. Since there are not >28 days in every month of the year, if the Month 1 injection occurred on the 29th, 30th, or 31st of the month, then the target study visit date for the remainder of the visits will be the 28th of the month.

The nominal target study visit day is derived as

- **M1 Target Day** = Date of Actual M1 Injection Visit Date – Date of First Oral lead-in Dose + 1, if subject receives M1 injection; else M1 Target Day = 30.
- **Mx Target Day** = Mx Nominal Target Study Visit Date – Date of First Oral lead-in Dose + 1, for x=2,3, ...

Assessment windows will be derived based on the midpoint between two consecutive planned target study visit dates. For the Snapshot efficacy data, the same approach will be used, except for Month 12, which will use a +/- 6-week window around the projected target study visit date at Month 12.

For parameters which are not scheduled to be assessed at visits, the all-inclusive assessment windows will still be used; however, data summaries will only report scheduled visits. Assessments at unscheduled visits will be included in summaries of worst-case values across visit (e.g. during the intervention phase) and in data listings, as well any algorithms that make use of additional data (e.g., Snapshot).

For participants transitioning to commercial product at EOS, the safety follow-up visit date will be the last date referenced and serve as the ending timepoint for the final visit window.

Table 1 Assessment Windows for Screening, Intervention and Extension Phase Data (Excluding HIV-1 RNA)

Target (Study Day)	Analysis Window		Analysis Timepoint
	Beginning Timepoint	Ending Timepoint	
Day of earliest record	Assessment Study Day ≤ 1		Screening
For subjects discontinuing prior to receiving first injection:			
30	Assessment Study Day = 2	Study Day of Last CAB/RPV Oral Dose+1	Month 1
	Assessment Study Day > (Study Day of Last CAB/RPV Oral Lead-in Dose +1)		Follow-up
For subjects receiving first injection:			
Day of First Injection	Study Day = 2	M1 target day + $\text{floor} [(M2 \text{ target day} - M1 \text{ target day})/2]$	Month 1
M2 Target Day	M1 target day + $\text{floor} [(M2 \text{ target day} - M1 \text{ target day})/2] + 1$	M2 target day + $\text{floor} [(M4 \text{ target day} - M2 \text{ target day})/2]$	Month 2
M4 Target Day	M2 target day + $\text{floor} [(M4 \text{ target day} - M2 \text{ target day})/2] + 1$	M4 target day + $\text{floor} [(M6 \text{ target day} - M4 \text{ target day})/2]$	Month 4
M6 Target Day	M4 target day + $\text{floor} [(M6 \text{ target day} - M4 \text{ target day})/2] + 1$	M6 target day + $\text{floor} [(M8 \text{ target day} - M6 \text{ target day})/2]$	Month 6
M8 Target Day	M6 target day + $\text{floor} [(M8 \text{ target day} - M6 \text{ target day})/2] + 1$	M8 target day + $\text{floor} [(M12 \text{ target day} - M8 \text{ target day})/2]$	Month 8
M10 Target Day	M8 target day + $\text{floor} [(M10 \text{ target day} - M8 \text{ target day})/2] + 1$	M10 target day + $\text{floor} [(M12 \text{ target day} - M10 \text{ target day})/2]$	Month 10
M12 Target Day	M10 target day + $\text{floor} [(M12 \text{ target day} - M10 \text{ target day})/2] + 1$	M12 target day + $\text{floor} [(M14 \text{ target day} - M12 \text{ target day})/2]$	Month 12
Mx Target Day	M(x-2) target day - $\text{floor} [(Mx \text{ target day} - M(x-2) \text{ target day})/2] + 1$	Mx target day + $\text{floor} [(M(x+2) \text{ target day} - Mx \text{ target day})/2]$	Month x For x = 14, 16, etc.
For subjects who permanently discontinue study treatment:			
	Assessment Study Day > Min (LTFU ART Start Date, Max (Study Day of Last Dose of Oral Study Treatment (CAB+RPV or SOC Bridging) + 1, Study Day of Last CAB + RPV Injection + 63))		Follow-up

Table 2 Assessment Windows for Screening and Intervention Phase HIV-1 RNA Data

Target (Study Day)	Analysis Window		Analysis Timepoint
	Beginning Timepoint	Ending Timepoint	
Day of earliest record	Assessment Study Day \leq 1		Screening
For subjects discontinuing prior to receiving first injection:			
28	Assessment Study Day = 2	Study Day of Last Oral Lead-in Dose +1	Month 1
	Assessment Study Day > (Study Day of Last CAB/RPV Oral Lead-in Dose + 1)		Follow-up
For subjects receiving first injection:			
Date of First Injection	Study Day = 2	M1 target day + $\text{floor} [(M2 \text{ target day} - M1 \text{ target day})/2]$	Month 1
M2 Target Day	M1 target day + $\text{floor} [(M2 \text{ target day} - M1 \text{ target day})/2] + 1$	M2 target day + $\text{floor} [(M4 \text{ target day} - M2 \text{ target day})/2]$	Month 2
M4 Target Day	M2 target day + $\text{floor} [(M4 \text{ target day} - M2 \text{ target day})/2] + 1$	M4 target day + $\text{floor} [(M6 \text{ target day} - M4 \text{ target day})/2]$	Month 4
M6 Target Day	M4 target day + $\text{floor} [(M6 \text{ target day} - M4 \text{ target day})/2] + 1$	M6 target day + $\text{floor} [(M8 \text{ target day} - M6 \text{ target day})/2]$	Month 6
M8 Target Day	M6 target day + $\text{floor} [(M8 \text{ target day} - M6 \text{ target day})/2] + 1$	M8 target day + $\text{floor} [(M10 \text{ target day} - M8 \text{ target day})/2]$	Month 8
M10 Target Day	M8 target day + $\text{floor} [(M10 \text{ target day} - M8 \text{ target day})/2] + 1$	M12 target day - 43	Month 10
M12 Target Day	M12 target day - 42	M12 target day + 42	Month 12
M14 Target Day	Assessment Study Day > M12 target day + 42		Month 14
For subjects who permanently discontinue study treatment during the Intervention Phase:			
	Assessment Study Day > Min (LTFU ART Start Date, Max (Study Day of Last Dose of Oral Study Treatment (CAB+RPV or SOC Bridging) +1, Study Day of Last CAB + RPV Injection + 63))		Follow-up

Table 3 Assessment Windows for Extension Phase HIV-1 RNA Data

Target (Study Day)	Analysis Window		Analysis Timepoint
	Beginning Timepoint	Ending Timepoint	
M14 Target Day	Study Day of Nominal Week 14 Visit	M14 target day - floor [(M16 target day – M14 target day)/2]	Month 14
M16 Target Day	M14 target day - floor [(M16 target day – M14 target day)/2] + 1	M16 target day + floor [(M18 target day – M16 target day)/2]	Month 16
Mx Target Day	M(x-2) target day - floor [(Mx target day – M(x-2) target day)/2] + 1	Mx target day + floor [(M(x+2) target day – Mx target day)/2]	Month x For x =18, 20 etc.
For subjects who permanently discontinue study treatment during the Extension Phase:			
	Assessment Study Day > Min (LTFU ART Start Date, Max (Study Day of Last Dose of Oral Study Treatment (CAB+RPV or SOC Bridging) +1, Study Day of Last CAB + RPV Injection + 63))		Follow-up

Table 4 Assessment Windows for Study Visit Length Data (Intervention and Extension Phase)

Target (Study Day)	Analysis Window		Analysis Timepoint
	Beginning Timepoint	Ending Timepoint	
Study Day of Actual M1 Injection	Study Day of Actual M1 Injection		Month 1
Study Day of Actual M2 Injection	Study Day of Actual M2 Injection		Month 2
Study Day of Actual M6 Injection	Study Day of Actual M6 Injection		Month 6
Study Day of Actual M8 Injection	Study Day of Actual M8 Injection		Month 8
Study Day of Actual Mx Injection	Study Day of Actual Mx Injection		Month x For x=17, 20, etc.
	If none of the above, then Analysis Timepoint = Other		

Table 5 Assessment Windows for Summaries of Long-Term Follow-up Phase Data from Subjects who Received at Least One Injection of CAB+RPV and Permanently Discontinued from the Study

Day of Assessment	Assessment Window	Target LTFU Study Day of Window
$1 \leq \text{LTFU Study Day} \leq 135$	LTFU Month 3	90
$136 \leq \text{LTFU Study Day} \leq 225$	LTFU Month 6	180
$226 \leq \text{LTFU Study Day} \leq 315$	LTFU Month 9	270
$316 \leq \text{LTFU Study Day} \leq 405$	LTFU Month 12	360
$(30*m-44) \leq \text{LTFU Study Day} \leq (30*m+45)$	LTFU Month m M = 15, 18, 21	30*m

- LTFU Study Day is defined in 13.5.1

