To assess fidelity to CAB LA + RPV LA injection dosing windows	Percentage of injections occurring within target window from the target date.
Evaluate efficacy and safety measures of CAB LA + RPV LA	Proportion of participants with plasma HIV-1 RNA <50 c/mL over time. Proportion of participants with confirmed virologic failure (CVF) over time Incidence of treatment-emergent genotypic and phenotypic resistance to CAB and RPV in patient study participants with CVF

Objectives	Endpoints/Estimands
	Incidence and severity of AEs, SAEs and proportion of participants who discontinue treatment due to AEs over time
To assess preference between CAB LA + RPV LA and oral ART medication received prior to entering the study	Preference between CAB + RPV LA and daily oral ART medication (received prior to entering the study) at quantitatively assessed via preference questionnaire at Dose 7

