13.4.2. Reporting Standards

General	

 The current GSK Statistical Display Standards in the GSK Standards Library (IDSL) will be applied for reporting, unless otherwise stated (Library Location: https://spope.gsk.com/sites/IDSLLibrary/SitePages/Home.aspx): 
 4.03 to 4.23: General Principles 5.01 to 5.08: Principles Related to Data Listings 6.01 to 6.11: Principles Related to Summary Tables 7.01 to 7.13: Principles Related to Graphics 	
Formats	

 GSK Statistical Display Principles (5.03 & 6.06.3) for decimal places (DP's) will be adopted for reporting of data based on the raw data collected, unless otherwise stated. Numeric data will be reported at the precision collected on the eCRF. The reported precision from non eCRF sources will follow the GSK Standard Statistical Display Principles but may be adjusted to a clinically interpretable number of DP's. 	
Planned and Actual Time	

 Reporting for tables, figures and formal statistical analyses: 
 Planned time relative to dosing will be used in figures, summaries, statistical analyses and calculation of any derived parameters, unless otherwise stated. The impact of any major deviation from the planned assessment times and/or scheduled visit days on the analyses and interpretation of the results will be assessed as appropriate. Reporting for Data Listings: 
 Planned and actual time relative to study drug dosing will be shown in listings (Refer to GSK Standard Statistical Display Principle 5.05.1). Unscheduled or unplanned readings will be presented within the participant's listings. 	

Unscheduled Visits	

 • Unscheduled visits will be assigned to an analysis visit using the all-inclusive windows defined in Section 13.2. • However, data summaries will only report visits that are planned assessment time points for each parameter (according to the Schedule of Activities in Section 13.1.1). • Evaluable assessments at unscheduled visits will be used when categorizing values across visits, such as 'maximum grade during the intervention phase' or 'at any time post-baseline', and for any algorithm that has specific rules for which observation to use (e.g. snapshot algorithm or CVF identification). 	
Descriptive Summary Statistics	

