13.12.8. Safety Figures

Safety: Figures					
No.	Population	GSK Standard / Example Shell	Title	Programming Notes	Deliverable
Adverse Events					
3.1.	Safety	201584/primary_07/F3.14	Plot of Incidence of Study Drug Injection Site Reaction Adverse Events by Implementation Arm and Visit (Overall and Common) – CAB and/or RPV	Sort by CAB+RPV, CAB, then RPV ISR onset assigned to most recent IM injection Visit	M12, EOS
CCI					
Laboratory					
3.3.	Safety	LIVER14	Scatter Plot of Maximum vs. Baseline for ALT	GSK Statistical Display Standard	M12, EOS
3.4.	Safety	LIVER9	Scatter Plot of Maximum Total Bilirubin vs Maximum ALT – eDISH Plot	GSK Statistical Display Standard	M12, EOS

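### By-visit AE tables slot events by midpoint windows, so about half the days after Dose 1 carry the label of an injection visit not yet reached and the Month 1 row is mostly oral lead-in

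*SAP*

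**What the plan says.** SAP 13.2.1 lists AEs among the data that "Laboratory data, vital signs, adverse events, and genotypic/phenotypic data will be assigned to assessment windows according to actual dates" governs, and then states: "Assessment windows will be derived based on the midpoint between two consecutive planned target study visit dates". Table 1 in that section starts the Month 1 window at Study Day 2 for anyone who receives a first injection. It ends each window half an interval after the target day and labels everything up to and including Study Day 1 as Screening. The Month 8 row takes its end from the Month 12 target, although the next visit is Month 10.

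Two reporting rules follow. In 13.2.1, "data summaries will only report scheduled visits". In 13.4.2, under unscheduled visits, "data summaries will only report visits that are planned assessment time points for each parameter", with reference to the schedule in 13.1.1. The AE row of that schedule has no entry at Months 2, 6 and 10, and footnote d says that "AE and SAEs will not be proactively assessed at M 2, M 6 and M 10". The same footnote requires any AE that a participant reports to be recorded at every visit.

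The endpoint is "Incidence and severity of AEs, SAEs and proportion of participants who discontinue treatment due to AEs over time" (SAP 2.2). Tables 3.17, 3.26, 3.31 and 3.35 show AEs by visit, and none has a programming note that overrides 13.2.1. Table 3.17 is a headline deliverable. Figure 3.1, for injection site reactions, uses another rule: "ISR onset assigned to most recent IM injection Visit".

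**The concern.** A midpoint window suits a measurement taken at a visit, because the nearest visit is the one it belongs to. An AE has its own onset date, and a reader of a by-visit table in this trial will take each row as following that visit's injection. Under the midpoint rule, an AE in the later part of a dosing interval appears under the next visit, before that dose has been given. The Month 1 row mixes tablet exposure with the first two weeks or so after Dose 1.

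The effect extends to stopping events. After permanent discontinuation, Table 1 keeps data in the visit windows until the earlier of the start of follow-up ART and the end of on-treatment time (at least 63 days after the last injection). An AE that ends treatment a month or more after the last injection can therefore sit under an injection visit that never took place. That bears on Table 3.35 and on the discontinuation part of the endpoint.

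At stake is how the SAP's AE-over-time displays are read, not whether events are captured.

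**Working it through.** **Inputs.** The SAP gives no figure of its own here, so the windows were rebuilt from its rules.
- First injection on 7 July, from the SAP example: "if Month 1 occurred on July 7th, all subsequent visits are expected to occur on the 7th of each month".
- Assumed: year 2021 and first oral dose on 7 June (30-day lead-in), so the first injection falls on Study Day 31. Every later dose is assumed to be on its target date.
- Study Day = date − first oral dose date + 1 (SAP 13.5.1).
- For consecutive visits a and b with target days T(a) and T(b): window a ends at T(a) + floor[(T(b) − T(a))/2], and window b starts the next day (Table 1). Month 1 starts at Day 2.

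**Windows.** The Month 8 end is taken at the Month 8–10 midpoint, with the printed version in brackets.

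| Visit | Target day | Window | Length | Days before target |
|---|---|---|---|---|
| Month 1 | 31 | 2–46 | 45 | 29 |
| Month 2 | 62 | 47–92 | 46 | 15 |
| Month 4 | 123 | 93–153 | 61 | 30 |
| Month 6 | 184 | 154–215 | 62 | 30 |
| Month 8 | 246 | 216–275 (printed 216–306) | 60 | 30 |
| Month 10 | 305 | 276–335 | 60 | 29 |
| Month 12 | 366 | 336–396 | 61 | 30 |

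**1. Days labelled with a visit not yet reached.** Months 2 to 12: 15 + 30 + 30 + 30 + 29 + 30 = 164. Days from Dose 1 to the Month 12 target: 366 − 31 = 335. Share: 164/335 = 49%.

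**2. Lead-in inside Month 1.** 31 − 2 = 29 of 45 days, or 64%.

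**3. Study Day 1.** Table 1 assigns Day 1 and earlier to Screening. Table 7 counts an AE as Screen only if its onset precedes the treatment start date, and that date is Day 1. A Day 1 AE is thus in the Intervention Phase without an Intervention Phase window.

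**4. Month 8 overlap.** Printed end: 246 + floor[(366 − 246)/2] = 306. Month 10 starts at 276. Days 276 to 306 lie in both windows: 31 days.

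**5. Months 2, 6 and 10, read literally.** 46 + 62 + 60 = 168 of 395 window days = 42.5%. With the printed Month 8 end, 31 of these days also fall in Month 8, so (168 − 31)/395 = 137/395 = 34.7% fall only in the omitted windows.

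**Range.** Over all 365 start dates in 2021 and assumed lead-ins of 28, 30 or 35 days: item 1 is 48.8–49.1%; item 2 is 63–69%; the overlap is 29–31 days; item 5 is 41.6–42.9%, or 33.8–35.1% exclusively.

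**Under the last-injection rule.** No day carries a later visit's label. The 164 days in item 1 change label, and the 29 lead-in days leave Month 1.

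**The case against.** A window supplies a visit label and says nothing about cause. Relatedness comes from the eCRF, and SAP 13.5.4 counts days since last dose from the last dose on or before onset. Both drugs can be detected for a year or longer after injections stop (protocol 8.5.5.4), so showing AEs by calendar position is defensible. This stands against any reading that the SAP attributes events to the wrong dose. It does not rescue the display, because the rows are named after dosing visits and Month 1 pools two routes of administration.

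A reader might infer that tablet and injection events cannot be told apart. The documents do not support that. Table 12 cuts AEs at the first injection, and Tables 3.13, 3.20, 3.28 and 3.33 report the lead-in separately.

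A reader might also infer that AEs at Months 2, 6 and 10 will be dropped. That is only a literal reading. The 13.2.1 sentence concerns parameters without scheduled assessments, and the 13.4.2 sentence concerns unscheduled visits. The protocol schedules injection site assessment at every injection visit, and the visible SAP schedule has a redaction where that row would be. The shell for Table 3.17 comes from another study and is not in the documents, so its visit rows are unknown. Even if the rows were left out, Tables 3.9, 3.11, 3.19, 3.27 and 3.32 are also headline outputs, are not split by visit, and keep the events.

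Figure 3.1 covers only injection site reactions, so it was never going to match the four tables overall. Only the injection site rows would be slotted differently. Other injection site tables are redacted and cannot be judged.

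**Conclusion.** The point holds for Tables 3.17, 3.26, 3.31 and 3.35. By the printed rule, about 49% of days between Dose 1 and the Month 12 target carry a later visit's label, and about 64% of the Month 1 window is oral lead-in (63–69% over the range tried). The Day 1 conflict and the Month 8 overlap are inconsistencies in the text; the overlap means one AE can fall in two windows. The possible omission of Months 2, 6 and 10 (about 42% of window days, or about 35% exclusively as printed) depends on a literal reading that the sponsor may not intend.

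All percentages are shares of days, and the documents give no AE counts by day from which to state a share of events. They assume dosing on target dates. It would go too far to say that safety reporting as a whole omits follow-up or misattributes events. The point still deserves a change, because these tables serve a secondary endpoint, one is a headline output, and the sponsor already applies a better rule elsewhere in the SAP.

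**What to change.** - Take AEs out of the midpoint windows in 13.2.1.
- For Tables 3.17, 3.26, 3.31 and 3.35, define an oral lead-in row running from the first oral dose, including Day 1, to the day before the first injection, as in Table 12. Assign each later AE to the last injection on or before onset, the rule Figure 3.1 uses for injection site reactions.
- Where a dose was missed or bridged, keep the AE with the last injection received. The phase rules in Table 7 and the on- and post-treatment rules in Table 11 continue to apply.
- State that every injection interval is shown, including Months 2, 6 and 10.
- For data still slotted by Table 1, end Month 8 at the Month 8–10 midpoint. Check also the general row for Month 14 onward, whose start subtracts the half-interval where the earlier rows add it.

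The cost is SAP wording and a small amount of derivation code, with no new data. The downside is that AE rows will no longer line up with the laboratory visit windows, which a footnote can explain.
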